Economic theory predicts that increases in life expectancy should lead to more forward-looking behavior [1]. Individuals who face a higher probability of living to future periods are expected to invest more resources in education and job training today, in order to enjoy greater total consumption over their lifetime. Similarly, with greater longevity, individuals are less likely to take risks – e.g. drunk driving, smoking, or sex work – that jeopardize their enjoyment of future utility. In spite of its theoretical appeal, the evidence on a causal link between subjective life expectancy and economic behavior is limited [2-4], particularly related to young adults and HIV. Perhaps the strongest evidence comes from a study in rural Malawi which found that scale-up of antiretroviral therapy led to increased survival expectations, greater labor supply, and greater human capital investment and savings [5,6]. However, without randomization of ART scale-up it is possible that other factors could have confounded this relationship.

Antiretroviral treatment (ART) for HIV has dramatically reduced mortality due to HIV/AIDS, turning what was once a death sentence into a manageable chronic condition. In rural KwaZulu-Natal, roll out of ART in the public sector has led to large gains in adult life expectancy, with gains of 18 years since 2003 (update of [name], et al. 2013 [7]). These changes may have widespread impacts on community norms, perceptions, and behaviors. Indeed, nearly 40% of community members in the area

live in a household or compound with someone who has sought care in the government ART program [8]. These longevity improvements likely influence how young adults think about their future. Little is known, however, about young adults' health perceptions in the age of ART and how perceptions affect health behaviors and feedback to the HIV epidemic itself. This increase in life expectancy may raise incentives for young adults to engage in preventive health behaviors – e.g., testing and linkage to HIV care – and future oriented behaviors like schooling and savings. However, limited information about these survival changes and bandwidth constraints to acquire this information [9] may minimize the impact these changes population changes in survival have on behavior. Young adults that are fatalistic about their future or believe they have low chances of survival may not perceive benefits to preventive health behaviors.

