The study is a population-based randomized controlled trial. To reduce potential for contamination, treatment assignment will be determined at the level of the household, such that if there are multiple eligible participants per household, they will receive the same treatment. Households will be randomized to study arm *ex ante*, i.e. before going into the field. *Ex ante* randomization has two benefits. First, as a quality control, *ex ante* randomization limits the opportunity for violations of treatment assignment. Second, because the study is nested in the AHRI population surveillance, *ex ante* randomization enables us to achieve balance across study arms with respect to several baseline characteristics of interest among eligible participants. We will use a constrained randomization approach to achieve approximate balance on: sex, age, whether the person was in school, orphans status, HIV positive status, HIV negative status (unknown is the third category), and household asset quintile. These factors were selected because of their potential influence on survival expectations. (For further details on randomization procedures, please see Appendix C.)

We note that sampling and randomization will be conducted using AHRI's public use (de-identified) data. We will provide a list of public use identifiers and treatment assignments to AHRI's data management staff, and they will create an operational database to be used during data collection. Information on the characteristics above (e.g. HIV status) will never be linked with personally-identifiable information.

Participants will be randomized using a ratio of 50% active treatment, 25% attention placebo control, 25% pure control.

	Active Treatment Video	Attention Placebo Video
Arm 1, Active Treatment	X	
Arm 2, Attention Placebo Control		X
Arm 3, Pure Control		

A8.3. Blinding

Participants and interviewers

During recruitment, consent, and the first half of the baseline survey, participants and interviewers will be blinded as to the participant's treatment assignment. Randomized treatment assignment will be revealed at the moment when participants received the intervention. However, we will not indicate to the participants whether the video they see is the treatment or attention placebo video.

Researchers

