The researchers will be blinded to the randomization status of participants throughout the data collection, extraction, and cleaning/quality control process, up until the date when randomized assignments are unmasked. To maintain blinding of treatment assignments vis-à-vis the research team during the study, we will use the following procedures:

- Treatment assignment will be stored as a hidden field in the REDCap database. I.e. during the baseline survey it will generate a pop-up message telling the interviewer to show the participant the active treatment video, active control video, or no video, however this field will not be visible to anyone on the research team.
- The treatment assignment field will not be exported during routine quality control procedures.
- Treatment assignment will be extracted along with study ID into its own table and will not be merged with any of the other data until randomization is unblinded.
- Randomization will be unblinded only after the final Pre-Analysis Plan is posted to www.clinicaltrials.gov. In developing our pre-analysis plan, we conducted some descriptive analysis of the blinded baseline pre-intervention survey data. Additionally, we monitored overall levels of uptake of the HIV testing voucher and job search training workshop in order to determine potential statistical power with these outcomes. For guidance on using baseline data to inform Pre-Analysis Plans, see Olken (2015).
- We will submit an update to our clinicaltrials.gov study profile after treatment assignment is unblinded, noting the date when we have done so.

As this is a short (4-month) pilot study and the intervention is minimal risk, we do not have a DSMB and do not have stopping rules for the trial based on preliminary analysis of efficacy.

A9. Baseline interview and intervention

The baseline survey visit is designed to take about 1.5 hours, and consists of the following sub-components:

A9.0. Recruitment and Informed Consent

Potential respondents will be recruited via visits to their homesteads. Permission will be obtained from the head of household to enter and to speak to the sampled participant. The study will be described and participants will provide written informed consent to participate in the study, including the baseline visit, a follow-up visit, and permission to link with demographic surveillance data. See Appendix B for the approved consent form.

A9.1. Survey module

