We will additionally assess balance on all primary and secondary outcomes described above that are measured at baseline.

Through linkage to the AHRI surveillance, we will additionally assess balance on: whether the person has a child; household size; distance to the nearest clinic, whether anyone in the household died from HIV in the prior 10 years; whether anyone in the household is receiving public sector ART at time of baseline.

For each baseline covariate, we will report a t-test for the null hypothesis of equal means in Arm 1 vs. Arms 2+3 (pooled).

B4. Statistical analysis of treatment effects

All statistical analyses will involve comparisons across the treatment arms described above. For each outcome, we will generate the following data:

Example Results Table (fake data)

	Sample Means				Treatment Effect Estimate (95% CI)		
	Arm 1, n=XXX	Arms 2+3, n=XXX	Arm 2, n=xxx	Arm 3, n=xxx	Crude difference	Adjusted for design variables ^a	Adjusted for design, strong predictors, and baseline imbalance ^b
Outcome 1	1.2	1.5			-0.3 (-0.5 to 0.2)	-0.3 (-0.5 to 0.2)	-0.3 (-0.5 to 0.2)
			1.7		-0.5 (-0.8 to 0.0)*	-0.5 (-0.7 to 0.0)*	-0.5 (-0.7 to 0.0)*
				1.4	-0.3 (-0.5 to 0.3)	-0.3 (-0.5 to 0.2)	-0.3 (-0.5 to 0.2)
Outcome 2							
...							
Outcome k							

^aDesign variables are those variables on which balance was explicitly assessed during randomization. ^bStrong predictors of the outcome are those factors in the baseline balance table that are adjusted differences include regression adjustment for stratifying variables, variables used in the constrained randomization, and variables that were not balanced at baseline despite randomization (p-value <0.1 in F-test).

Sample means will be reported for Arm 1, the combined control (Arms 2+3), and for Arm 2 and 3 separately. When assessing changes from baseline to follow-up, we will simply define the outcomes as within-subject “differences” to facilitate comparisons with other outcomes observed only after the intervention.

Crude comparisons of outcomes between treated and comparison arms will be assessed in linear regression models, regressing the outcome on an indicator for treatment arm and indicators for week-block, a stratification variable. We will adjust our standard errors for clustering at the household level, given that error terms without households may be correlated.

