Logistic regression model. We will also estimate our primary models using multivariate logistic regression to assess sensitivity to specification. In lieu of odds ratios, we will report marginal effects associated with the treatment arm, to enable comparison with the estimate from the OLS models. Again, standard errors will be clustered at the household level.

Restrict to HIV-uninfected. HIV testing uptake – one of our primary outcomes – is less relevant for individuals who already know their current HIV status. In a robustness check, we will assess HIV uptake after excluding: individuals who reported that they had ever tested for HIV and were certain that they were HIV positive at baseline (20 out of 20 beans); and individuals who reported testing for

HIV in the prior 3 months and reported that they were sure that they were HIV negative (0 out of 20 beans).

Remove participants with inconsistent answers and extreme outliers. A small number of participants reported inconsistent answers to the survival expectations questions at baseline. We will assess robustness of results after removing: participants who reported non-zero chances of survival at ages greater than the “oldest possible age” they could imagine living to; participants who reported that it was unlikely they would live to 60 years but allocated >10 beans; participants who reported that it was likely they would live to 60 years but allocated <10 beans. Demographic differences between persons with consistent and inconsistent answers will be reported.

B7. Adjusting Inference for Multiple Hypothesis Testing

No adjustments will be made for our primary outcomes.

For secondary outcomes, the primary manner in which we adjust for multiple hypotheses being tested is by grouping outcomes into indices such that their joint significance will be tested. If we do not find that there is overall significance for aggregated measures of behaviors such as local of control, we will not move test statistical significance of individual index components. In addition, for families of outcomes where we are interested in testing the treatment effect both for an index overall as well as individual components, when the number of tests is large (greater than 10), we adjust our standard errors using the Benjamini-Hochberg procedure[24] for controlling the false discovery rate to less than 0.05.

B7. Handling attrition

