Appendix A. Sampling Strategy

Appendix B. Consent Form

Appendix C. Randomization Procedures

Appendix A. Sampling Strategy

Sampling Protocol

The sampling frame was all young adults who resided in bounded structures located in PIPSA week blocks 33-41 and were part of the AHRI PIPSA eligibility list. Young adults were defined as individuals who were 18 years or older on August 15, 2017 and were 25 years or younger on October 1, 2017. Week blocks 34-41 were selected because the AHRI surveillance was scheduled to visit these weekblocks for the annual surveillance visit and HIV testing 4 weeks after we would be there. With the AHRI surveillance 2 weeks behind schedule, we are expecting our respondents to be visited by the surveillance 4-6 weeks after the baseline survey visit. The AHRI eligibility list includes those known to reside in the surveillance and includes all those who resided in the surveillance at last visit in 2016 as well as some known to have moved in.

We randomly sampled Bounded Structures within each week block and included all individuals in each Bounded Structure. We proceeded until we had 120 individuals per Week Block, or 20 per field worker per week. We anticipate that each field worker will be able to complete 10-15 interviews per week.

The target sample size for interviews completed was 450. We assumed a 62.5% response rate, which is similar to prior studies of young adults at AHRI. Based on this response rate, we estimated that we needed to sample 720 individuals to complete 450 interviews. With a 6-field worker team and 2.5 interviews conducted per field worker per day, we project that the baseline survey will be completed in six weeks.

We sampled 8 weeks of data to ensure that if unforeseen circumstances (e.g., difficulties locating respondents, fieldworker absences, etc.) dictate lower productivity, then we will have respondents already sampled to finish fieldwork.

Our “stopping rule” for study enrollment is defined as: “Data collection will proceed for six weeks. If at the end of six weeks, we have not yet recruited 450 participants, then data collection will continue for a seventh week. If at the end of seven weeks, we have not yet recruited 450 participants, then data collection will continue for an eighth week. If after eight weeks, we still have not attained 450 participants, we will cease enrollment.”

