Appendix C. Randomization Procedures

Variables Randomized. Study participants are randomized with respect to:

- 1) Intervention video vs. no intervention video
- 2) Pure control vs. attention placebo control (among those randomized to no intervention video)
- 3) 20 Rand vs. 5 Rand cost to reserve spot at job search skills workshop
- 4) Male-vs.-female-oriented HIV transmission questions

1. Intervention video vs. no intervention video

Level of randomization. Individuals are randomized to video intervention vs. control. Randomization is at the bounded structure level, so that all respondents within a bounded structure get the same treatment.

Stratification. Randomization is stratified by weekblock to ensure approximately equal numbers of treated and controls within weekblocks.

Constrained (restricted) randomization. The AHRI data contain robust information on baseline covariates. However, because randomization is at the level of the bounded structure, it was not possible to stratify by individual characteristics. Instead, we use a constrained (aka restricted[25]) randomization approach. For the primary analysis – comparison of intervention video vs. no intervention video, we constrained randomization to force balance on the following characteristics: sex, age, whether the person was in school, orphan status, HIV positive status, HIV negative status (unknown is the third category), and household asset quintile. We randomized the intervention treatment assignment (intervention video vs. no intervention video) 3078 times using different randomization seeds. Each time, we assessed balance on key characteristics through a t-test (i.e regression of treatment assignment on the covariate). All randomization seeds that lead to a maximum t-test value greater than 1.68 ($p<0.1$) were excluded. This excluded 62% and retained 38% of the seeds (1060 seeds). We then randomly selected two seeds from these 1060 acceptable seeds. One was used to randomize the video, the other was used to randomized the incentive for the job search skills workshop. We assessed correlation of these two interventions and re-randomized if the Chi2 p-value for the cross-tab was less than 0.5 (see tables below).

2. Pure control vs. attention placebo control (among those randomized to no intervention video)

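### Appendix C randomises bounded structures, but sections B4 and B6 cluster standard errors by household, and nothing in the plan says the two units are the same

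*Combined protocol and SAP*

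**What the plan says.** Three parts of the document bear on the unit of assignment.

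- **Sampling (Appendix A):** "We randomly sampled Bounded Structures within each week block and included all individuals in each Bounded Structure".
- **Randomisation (Appendix C):** "Randomization is at the bounded structure level, so that all respondents within a bounded structure get the same treatment". The same appendix repeats the unit when it explains the constrained randomisation: "because randomization is at the level of the bounded structure, it was not possible to stratify by individual characteristics".
- **Randomisation (A8.2):** "treatment assignment will be determined at the level of the household". This section sends the reader to Appendix C for further detail.

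The analysis sections follow A8.2. B4 states for the linear models: "We will adjust our standard errors for clustering at the household level". B6 repeats it for the logistic models: "standard errors will be clustered at the household level".

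No section defines a bounded structure, says that each holds one household, or says that the terms are interchangeable.

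**The concern.** Cluster-robust standard errors should be computed at the unit that was assigned, or at a coarser one. Appendix C is the fuller account and reports what was done, including the number of seeds drawn and the arm counts by week-block. On that record the unit is the bounded structure.

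If a structure can contain two households with eligible young adults, those households share an assignment. Household clustering then treats them as independent. With positively correlated outcomes, the standard error for the primary contrast, Arm 1 versus Arms 2+3, is too small.

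Two lesser points sit beside this:

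- B3 plans a t-test for each baseline covariate without mentioning clustering, and B4(c) selects adjustment covariates from those tests at p<0.1.
- Appendix C describes simple randomisation of respondents between Arm 2 and Arm 3 and does not say whether structures were kept together. A8.2 promises one treatment per household. This affects only the secondary comparisons.

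**Working it through.** **The plan's own figure.** A7 gives 450 participants, 80% power and a detectable difference of 0.26 SD. With 225 per side and two-sided 5% (assumed, since no level is stated), (1.960 + 0.842) × √(2/225) = 0.264 SD, which rounds to the stated value. No clustering allowance is needed to reach it, so it does not depend on which unit is right.

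**Inputs.** From the documents: n = 450, 1:1 for the primary contrast; response r of 50–60% (A7) or 62.5% (Appendix A). Assumed, because the documents give no figures:

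- q, the share of sampled structures holding two eligible people from different households (all others hold one): 5–30%.
- ρ, the correlation between those two people: 0.1–0.3.
- Response is independent between people.

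**Step 1: share of recruited structures with both people recruited.** s = q·r / [1 + q(1 − r)].

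- Low: 0.05 × 0.5 / (1 + 0.05 × 0.5) = 0.024.
- High: 0.30 × 0.625 / (1 + 0.30 × 0.375) = 0.169.

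**Step 2: design effect missed by household clustering.** D = 1 + 2sρ/(1 + s).

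- Low (ρ = 0.1): 1 + 2 × 0.0244 × 0.1 / 1.0244 = 1.0048.
- High (ρ = 0.3): 1 + 2 × 0.1685 × 0.3 / 1.1685 = 1.0865.

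**Step 3: consequence.** Type I error = 2[1 − Φ(1.96/√D)], and correct half-width = 1.96 × √(4D/450).

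| Case | D | Type I error | Half-width (SD) |
|---|---|---|---|
| Units coincide | 1 | 5.0% | 0.1848 |
| Low | 1.0048 | 5.05% | 0.1852 |
| High | 1.0865 | 6.0% | 0.1926 |

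**Step 4: simulation including the constrained randomisation.** There were 10,000 trials per case (Monte Carlo standard error about 0.2 points), with 720 people sampled in six blocks and r = 0.625. Structures were randomised 1:1 within block and redrawn until every |t| on seven covariates was below 1.68. It was further assumed that the asset covariate carries one third of the shared variance and that one balance covariate carries 10% of the individual variance. Rejection rates in %, household versus structure clustering:

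| q, ρ | Adjusted model | Crude model |
|---|---|---|
| q = 0 | 5.0 vs 5.0 | 4.6 vs 4.6 |
| 0.05, 0.1 | 4.8 vs 4.8 | 4.2 vs 4.1 |
| 0.10, 0.3 | 5.75 vs 5.4 | 4.9 vs 4.5 |
| 0.30, 0.1 | 5.4 vs 5.2 | 5.1 vs 4.8 |
| 0.30, 0.3 | 5.9 vs 5.05 | 5.15 vs 4.4 |

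The gap is at most about 0.9 points in the adjusted model and about 0.75 in the crude one.

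**Step 5: what Appendix C's table implies.** Treated counts by week-block are 60, 60, 60, 59, 60, 60, 61 and 58, so the squared deviations from 60 sum to 0+0+0+1+0+0+1+4 = 6. Suppose half the structures in each block went to each arm, and each block held d two-person structures, so that q = d/(120 − d). The probability of a sum of 6 or less is then:

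- 0.37–0.39 at d = 3–4 (q about 3%)
- 0.05 at d = 10 (q = 9%)
- 0.03 at d = 12 (q = 11%)
- 0.004 at d = 30 (q = 33%)

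At q = 0.091, r = 0.625 and ρ = 0.3, s = 0.055, D = 1.031 and the type I error is 5.4%. At q about 3%, s = 0.019, D = 1.004–1.011 and the error is about 5.04–5.12%. If the allocation balanced persons rather than structures, the table says nothing about sharing.

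**The case against.** The ordinary reading may be that these are two labels for one unit. A8.2 and Appendix C state the same rule in parallel, one defers to the other, and B4 and B6 cluster at exactly the unit A8.2 names. A9.0 describes visits to homesteads and a single gatekeeper: "Permission will be obtained from the head of household to enter and to speak to the sampled participant". The one phrase that separates the terms, in A2, says people "live in a household or compound with someone who has sought care in the government ART program". That is background from a cited study and does not mention bounded structures. This reading is fair, but it remains an inference, because the plan nowhere states it.

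The numerical case is also weak. The sharing rates and correlations are assumptions. In the crude model the household-clustered test ran at 4.2–5.15%, so no inflation was shown there. At the most extreme setting, structure clustering took it from 5.15% to 4.4%, further from nominal. In the adjusted model at q = 0.10, part of the 5.75% is not due to the clustering unit, because structure clustering itself gave 5.4%. The 5.4% derived from the allocation table counts every two-person structure as two households, although same-household pairs are already handled. It therefore overstates the problem. All of this stands and supports a low rating.

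The side points add little. B3's silence on clustering is not a contradiction. Appendix C also speaks of individuals being randomised to the video just before it gives the structure as the unit, so its reference to respondents does not establish a person-level split of the controls.

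The objection does not remove the mismatch between the recorded unit of randomisation and the stated unit of clustering, or the case for a correction that is safe under either reading.

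**Conclusion.** The point holds and is minor. The plan does not demonstrate that its standard errors are clustered at the unit assigned, and no error in them has been shown. If the units coincide, no result changes. If they do not, and 5–30% of sampled structures hold two eligible people from different households with correlation 0.1–0.3, a nominal 5% test runs at about 5.05–6.0% and half-widths are understated by at most 0.1926/0.1848 − 1 = 4%. If structures were split equally within blocks, the allocation table puts the likely figure nearer 5.0–5.4%. Confidence is medium, because the number of households per structure is not reported.

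**What to change.** In B4 and B6, cluster standard errors on the bounded structure, citing Appendix C as the record of the unit randomised. This is valid whether or not structures and households coincide. Even at the highest sharing rate considered, about 450/1.169 = 385 structures would remain, so the number of clusters is not a difficulty.

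The following would usefully accompany it:

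- Define bounded structure against household in A8.2, and reconcile that section with Appendix C.
- Report structures, households and participants per arm.
- Use the same clustering in the B3 balance tests.
- State whether the Arm 2/Arm 3 split was made by respondent or by structure, and reconcile it with A8.2.

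A12 schedules unblinding for the day after posting. The change should therefore be recorded as a dated clarification that follows from the recorded randomisation and not from any result.

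The cost is a few lines of text and no new data collection. The structure identifier was used for sampling and randomisation, but the documents do not say that it is in the analysis file, so it may have to be re-linked by study ID.
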